### **Summary of the Research Proposal:**

Osteoporosis is a common bone disease characterized by decreased bone strength, leading to an increased risk of fractures. Affecting approximately 200 million patients worldwide, osteoporosis poses significant socioeconomic challenges and severe health impacts. The disease predominantly affects postmenopausal women due to the sharp decline in estrogen levels, crucial for maintaining bone density. However, it also occurs in men, especially the elderly. Early diagnosis is critical as osteoporosis often remains undetected until fractures occur, significantly impacting the quality of life and increasing mortality risk.

### **Study Objectives:**

1. **Proteomic and Metabolomic Analysis:**
  - **Clinical Samples:** Collect bone and serum samples from postmenopausal women with osteoporotic fractures and controls with hip osteoarthritis. Perform proteomic and metabolomic analyses to find disease-specific biomarkers and therapeutic targets.
2. **Identification of New Biomarkers:**
  - Identify proteins and metabolites that significantly differ between osteoporosis and control groups.
  - Correlate omics data with clinical markers of bone metabolism (e.g., CTX, PINP).
3. **Pathophysiological Mechanisms:**
  - Explore the underlying mechanisms of bone loss and remodeling in osteoporosis.
  - Develop a panel of potential omics biomarkers for osteoporosis.
4. **Therapeutic Target Identification:**
  - Use the data to evaluate new pharmacological targets for osteoporosis treatment at the clinical level.

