## **Research Methodology:**

- **Omics Technologies:** Employ proteomics and metabolomics for a non-targeted analysis of bone, plasma, and serum samples.
- **Data Integration:** Combine omics results with clinical data to create comprehensive profiles of osteoporosis.
- **Clinical Studies:** Utilize human clinical samples to validate findings and identify potential interventions.

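### The only named contrast, osteoporotic fracture versus hip osteoarthritis, mixes osteoporosis with fracture response and osteoarthritis, so by itself it does not support disease-specific or early-diagnosis claims

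*Protocol*

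**What the plan says.** Objective 1 of the Study Objectives defines the two groups: "Collect bone and serum samples from postmenopausal women with osteoporotic fractures and controls with hip osteoarthritis". It then states the purpose: "Perform proteomic and metabolomic analyses to find disease-specific biomarkers and therapeutic targets".

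Objective 2 refers to the same pair without the fracture and osteoarthritis qualifiers: "Identify proteins and metabolites that significantly differ between osteoporosis and control groups". Objective 3 is more cautious: "Develop a panel of potential omics biomarkers for osteoporosis". Objective 4 takes the results further: "Use the data to evaluate new pharmacological targets for osteoporosis treatment at the clinical level".

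Research Methodology adds two general statements: "Combine omics results with clinical data to create comprehensive profiles of osteoporosis" and "Utilize human clinical samples to validate findings and identify potential interventions". Expected Outcomes lists new markers for early diagnosis among the results. The Summary of the Research Proposal explains why early diagnosis matters: the disease tends to go unnoticed until a bone breaks.

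The protocol does not say whether controls have osteoporosis or whether cases have hip osteoarthritis. It names no group of women with osteoporosis who have not fractured.

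**The concern.** The two groups differ in at least three ways at once: osteoporosis, a fracture, and hip osteoarthritis. A protein or metabolite that differs between them may be following any of the three. The objectives attribute the difference to osteoporosis alone.

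Two consequences follow. Features that respond to fracture or to osteoarthritis can be reported as osteoporosis markers and then carried into the evaluation of drug targets in Objective 4. And a marker that appears only after a fracture cannot help to find the disease before one, which is the use the protocol gives as its reason for early diagnosis.

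The choice of groups and the labels put on the output are fixed in the protocol's objectives. They are not details that an analysis plan would normally settle.

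**Working it through.** The protocol gives no sample size, power or effect size, so there is no figure to reproduce. The check asks what the named groups can estimate.

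**Inputs.** From Objective 1: all cases have osteoporosis (OP) and a fracture (FX), and all controls have hip osteoarthritis (OA). Assumed: effects add, and no control has a fracture. Unknown: p, the share of controls with osteoporosis, and q, the share of cases with hip osteoarthritis.

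**Unadjusted difference.**
- Case mean (above a common intercept): OP + FX + q·OA
- Control mean: p·OP + OA
- Difference: (1−p)·OP + FX − (1−q)·OA

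Fracture enters this difference with full weight whatever p and q are. At p = 0 and q = 0 it is OP + FX − OA. At p = 1 osteoporosis cancels and FX − (1−q)·OA remains.

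**Estimability when p and q are recorded and used.** Each type of participant is a row (intercept, OP, FX, OA). An effect is estimable if adding its contrast leaves the rank unchanged.

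| Who is present | Rows | Rank (of 4) | Osteoporosis effect |
|---|---|---|---|
| p = 0, q = 0 | (1,1,1,0), (1,0,0,1) | 2 | not estimable |
| p = 0, 0 < q < 1 | (1,1,1,0), (1,1,1,1), (1,0,0,1) | 3 | not estimable; only OP + FX is |
| p = 1, q = 0 | (1,1,1,0), (1,1,0,1) | 2 | not estimable |
| 0 < p < 1, q = 0 | (1,1,1,0), (1,0,0,1), (1,1,0,1) | 3 | estimable |
| 0 < p < 1, 0 < q < 1 | (1,1,1,0), (1,1,1,1), (1,0,0,1), (1,1,0,1) | 4 | estimable |

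In the last two lines the osteoporosis effect comes from the same subtraction within controls: (1,1,0,1) − (1,0,0,1) = (0,1,0,0). Every case has osteoporosis, so cases carry no information that separates it from fracture.

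**Precision of the comparison within controls.** With n per group and common variance σ²:
- case versus control: SE = σ·√(2/n)
- osteoporotic versus non-osteoporotic controls: SE = σ·√(1/(np) + 1/(n(1−p))) = σ·√(1/(np(1−p)))
- ratio = √(1/(2p(1−p)))

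The shares below are assumed, since the protocol gives none.

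| p | 2p(1−p) | SE ratio |
|---|---|---|
| 0.1 | 0.18 | 2.36 |
| 0.2 | 0.32 | 1.77 |
| 0.3 | 0.42 | 1.54 |
| 0.5 | 0.50 | 1.41 |

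The two comparisons target different quantities. The ratio shows how imprecise the check within controls would be, not how large the confounding is.

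**What would separate the effects.** Start from the two named groups with p = 0 and q = 0. Adding only unfractured women with osteoporosis, (1,1,0,0), gives rank 3, and osteoporosis is still not estimable. Adding also unfractured women without osteoporosis or osteoarthritis, (1,0,0,0), gives rank 4, and osteoporosis and fracture are both estimable.

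**The case against.** The strongest reply is that this is a discovery study described in a short summary. Disease-specific states what the analysis hopes to find, the second objective's group names are shorthand for groups defined just above, Objective 3 speaks only of potential biomarkers, and Expected Outcomes describes a wider programme. Validation is also foreseen: "Utilize human clinical samples to validate findings and identify potential interventions". Much of this is fair, and the contrast is usable for finding candidates. But the hedge in Objective 3 does not reach Objectives 1 and 2 or Expected Outcomes, and the validation statement names no unfractured comparison.

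A second reply is that adjustment is normally left to the SAP and that clinical data are to be combined with the omics results. This stands in part. The full weight of fracture applies to the unadjusted difference only. If both p and q lie strictly between 0 and 1 and are recorded, all three effects are estimable under the additive model. The protocol does not say that this is so, and even then osteoporosis is identified only among controls, which is not the comparison that Objective 2 describes.

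A third reply is that every share used above is assumed. That is correct. The protocol supports a finding that the effects are mixed, not a bias of known size.

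**Conclusion.** The point holds and should be fixed. The unadjusted contrast does not by itself support the disease-specific label, the reading as osteoporosis against control, or the early-diagnosis outcome. Under an additive model with no fractures among controls, the osteoporosis effect is not estimable at any sample size if no control has osteoporosis. If some but not all do and it is recorded, the effect is estimable, but only from variation among controls.

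Three stronger readings are not supported:
- A reader might infer that osteoporosis can never be separated in this design. That depends on the controls' bone status, on which the protocol is silent.
- A reader might infer that the results will be biased by a known amount or in a known direction. The protocol gives no fracture or osteoarthritis effect on any analyte.
- A reader might infer that the planned correlation with turnover markers ("Correlate omics data with clinical markers of bone metabolism (e.g., CTX, PINP") carries the same mixture. That would require pooling the two groups, which the protocol does not state, so the point does not rest on it.

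**What to change.** - **(a)** In Objectives 1 and 2, name the contrast and its output as osteoporotic fracture versus hip osteoarthritis, and drop disease-specific.
- **(b)** In Objectives 1 and 2 and Expected Outcomes, describe hits as candidates. State that no early-diagnosis claim is made for a serum or plasma marker until it is confirmed in unfractured women with and without osteoporosis. Bone-tissue features stay candidate mechanisms or targets, because confirming them in unfractured women would need an extra procedure.
- **(c)** Where the controls' bone status is recorded, compare osteoporotic with non-osteoporotic osteoarthritis controls as a supportive check that a feature follows osteoporosis rather than fracture.

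**Cost.** (a) and (b) are wording and need no extra patients in this study. The price is a narrower conclusion, and the confirmation sample has to be found elsewhere. (c) uses the planned controls and needs only their bone status. It may be imprecise: at an assumed 10% of controls with osteoporosis, its standard error is about 2.4 times that of the main comparison. It also assumes that osteoporosis acts alike with and without osteoarthritis. If it does not, (c) estimates the effect of osteoporosis in women with osteoarthritis only, so it is a check and not proof.

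### Does correlating omics features with CTX and PINP in a two-group study build in correlations that reflect only group membership?

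*Protocol*

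**What the plan says.** Study Objectives, item 1, sets up two groups: "Collect bone and serum samples from postmenopausal women with osteoporotic fractures and controls with hip osteoarthritis". Item 2 has two bullets of equal rank. One is to "Identify proteins and metabolites that significantly differ between osteoporosis and control groups"; the other is to "Correlate omics data with clinical markers of bone metabolism (e.g., CTX, PINP"). Item 3 includes the aim to "Develop a panel of potential omics biomarkers for osteoporosis", and item 4 turns to pharmacological targets.

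Research Methodology adds that the assays are untargeted ("Employ proteomics and metabolomics for a non-targeted analysis of bone, plasma, and serum samples") and that the sponsor will "Combine omics results with clinical data to create comprehensive profiles of osteoporosis".

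The document has no analysis section. It states no sample size, significance level, test, type of correlation or covariates, and gives no CTX or PINP values for either group.

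**The concern.** The two bullets of item 2 are easily read as a sequence: first find the features that separate the groups, then support them by their correlation with bone turnover markers. If all participants were pooled for the second step, and CTX or PINP also differed between fracture and osteoarthritis patients, any feature that differs by group would correlate with the marker even if the two were unrelated within each group. The correlation would look like a second line of evidence while largely restating group membership. Features could then enter the panel or the target list as bone-related without any link to turnover inside either group. Nothing in the protocol rules this out, so the question is a natural one.

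**Working it through.** The protocol states no figure that could be reproduced. The check has two parts: how large the artefact could be, and whether the text commits to the analysis that produces it.

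**1. Size of the artefact, if the groups are pooled without adjustment**

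Inputs, all assumed: zero correlation within each group; share *p* of participants in one group; group differences *dx* (feature) and *dy* (CTX or PINP), in within-group SD units. Then

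pooled r = p(1−p)·dx·dy / √[(1 + p(1−p)·dx²)(1 + p(1−p)·dy²)].

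With equal groups, p(1−p) = 1/4:

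- dx = dy = 0.5: 0.0625/1.0625 = 0.06
- dx = dy = 0.8: 0.16/1.16 = 0.14
- dx = dy = 1.0: 0.25/1.25 = 0.20
- dx = dy = 1.5: 0.5625/1.5625 = 0.36
- dx = 1.0, dy = 0.5: 0.125/√(1.25 × 1.0625) = 0.11
- dy = 0, any dx: 0

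Simulated share of pooled correlations with p < 0.05, with the same difference in feature and marker (two runs where a range is shown for 0.8 and 1.0):

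| Difference in both | 60 participants in total | 100 participants in total |
|---|---|---|
| 0.8 SD | 18–19% | 28% |
| 1.0 SD | 33–35% | 52–53% |
| 1.5 SD | 85% | 97% |

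At 0.5 SD in both, the share is only 7% to 9% over these sample sizes. With adjustment for group, the simulated rates lie between 4.6% and 5.5%.

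A second simulation imitates an untargeted assay: 2000 features, 10% of them differing by 1 SD, features selected by t-test at p < 0.05, zero within-group correlation, 100 repetitions. Share of selected features whose pooled correlation reaches p < 0.05:

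| CTX/PINP difference | 20 per group | 30 | 50 | 100 |
|---|---|---|---|---|
| 0 | 5% | 5% | 5% | 5% |
| 0.5 SD | 11% | 12% | 15% | 25% |
| 1.0 SD | 24% | 30% | 42% | 62% |

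Without the selection step, the rate over all features at a 1.0 SD marker difference is 7% to 13%. Correlations centred within group stay at 4.8% to 5.2% in every cell. The result thus runs from no inflation to severe inflation, depending on inputs that the protocol does not supply.

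**2. What the text commits to**

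The artefact needs three conditions, and selecting features first makes it worse. Taking these in turn, with the role given to the result:

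- *Groups pooled and no group term.* The bullet names what is correlated with what. It does not say over which participants or with which adjustment.
- *Marker differs between groups.* The groups are defined by fracture and osteoarthritis, not by CTX or PINP, and no marker values or sampling times relative to fracture are given.
- *Feature differs between groups.* This is true by design of the features that the other bullet seeks.
- *Selection first.* The correlation bullet refers to the omics data in general. Neither order nor dependence between the two bullets is stated.
- *Correlation as a filter.* The panel and the targets stand under items 3 and 4. Neither these items nor Expected Outcomes makes entry depend on the correlation, and the integration line in Research Methodology gives no such rule either.

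Only the third of these can be read from the document. The others have to be supplied by the reader.

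**The case for a change.** The strongest case for the concern is that the correlation is a named part of an objective, and that pooled and within-group association are different questions rather than variants of one model. Read plainly, correlating the data collected means using both groups. A formal selection step is not needed for the artefact, because the features that differ by group are the candidate biomarkers in any case. The protocol also presents CTX and PINP as bone metabolism markers and contrasts a disease of bone loss with a control group, so a marker difference is plausible.

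Much of this stands. The mechanism is correct, the arithmetic holds, and a marker difference is not far-fetched. It would be good practice for the analysis plan to say whether the correlations are within group or adjusted for group, and which features enter. But a plausible reading is not a stated method. The same sentence is met equally well by a group-adjusted or stratified correlation, for which the rate is the nominal 5%. How large any marker difference would be cannot be taken from the document, and the argument that fracture healing alters turnover rests on knowledge from outside it.

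**Conclusion.** The concern does not hold. The protocol names a correlation with bone turnover markers without fixing how it is computed, so it neither states anything wrongly nor commits to a poor method. The choice between pooled, stratified and group-adjusted correlation is commonly left to the statistical analysis plan, and its absence from a short protocol summary is no error.

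The size of the risk is conditional. With zero within-group correlation and equal groups, pooled r runs from 0 when the marker does not differ to 0.20 at 1 SD and 0.36 at 1.5 SD in both variables. Adjustment for group removes the inflation. These figures rest on assumed differences and sample sizes. The conclusion rests on the wording of the protocol alone; a statistical analysis plan that prescribed pooled, unadjusted correlations as support for biomarkers would have to be judged afresh.

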## **Research Methodology:**

- **Omics Technologies:** Employ proteomics and metabolomics for a non-targeted analysis of bone, plasma, and serum samples.
- **Data Integration:** Combine omics results with clinical data to create comprehensive profiles of osteoporosis.
- **Clinical Studies:** Utilize human clinical samples to validate findings and identify potential interventions.

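### Does naming plasma in the methodology, but not among the samples collected under Objective 1, leave an analysis without a specimen or put the group comparison at risk?

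*Protocol*

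**What the plan says.** Two places in the protocol bear on this.

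- **Study Objectives, item 1 (Clinical Samples).** The instruction is: "Collect bone and serum samples from postmenopausal women with osteoporotic fractures and controls with hip osteoarthritis". The next sentence gives the purpose: "Perform proteomic and metabolomic analyses to find disease-specific biomarkers and therapeutic targets". It does not assign either platform to a specimen type.
- **Research Methodology, Omics Technologies.** Proteomics and metabolomics are to be used "for a non-targeted analysis of bone, plasma, and serum samples".

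The only other reference to specimens, under Clinical Studies in the same methodology section, is generic: "Utilize human clinical samples to validate findings and identify potential interventions". Plasma is named once in the document, in the methodology. The text at hand gives no sample size, significance level, or rule on combining specimen types.

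**The concern.** Read literally, the two lists disagree, and the difference matters in the laboratory. Serum comes from clotted blood and plasma from anticoagulated blood, so the tube has to be chosen before the draw and one cannot be made from the other afterwards. A site that followed Objective 1 to the letter would have no plasma for the methodology to use.

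The second worry is bias. Clotting removes fibrinogen and releases platelet contents, so some proteins and metabolites differ between serum and plasma whatever the patient's disease. The analysis is non-targeted, so no prior list would exclude such features. Fracture patients and patients with hip osteoarthritis may also be sampled in different settings. If plasma were used more often in one group, and plasma and serum results were analysed together, a matrix effect could pass for a disease effect and enter the biomarker panel.

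**Working it through.** **Comparing the lists.** The protocol states no figure to reproduce, so the first step is to set the lists side by side.

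| | Bone | Serum | Plasma |
|---|---|---|---|
| Collected (Study Objectives, item 1) | yes | yes | not named |
| Analysed (Research Methodology) | yes | yes | yes |

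The difference is one item, plasma. Is it a contradiction or an omission? A contradiction would require Objective 1 to exclude plasma, for example by limiting collection to bone and serum. It does not. Collecting bone, serum and plasma meets both sections in full. The methodology is also the place where one expects the fuller list, so a shortened list in the objective is at least as plausible as an analysis planned without material. Nor is it accurate to speak of three planned analyses, one of them lost: the section names two platforms applied to three sample types.

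**What the mixing bias would need.** All of the following would have to hold:

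1. plasma is drawn from some participants and not others;
2. its share differs between cases and controls;
3. plasma and serum values are analysed as one variable.

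The protocol states none of these. It lists the two matrices separately.

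**Size of the hypothetical.** Every input here is an assumption and none comes from the protocol: a matrix shift of 2 SD in one feature, a share of plasma differing by 25 or 50 percentage points, 30 participants per group, and a two-sided t test at 0.05.

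- Spurious difference = shift × imbalance: 2 × 0.25 = 0.5 SD and 2 × 0.50 = 1.0 SD.
- With the within-group SD held at 1, the noncentral t distribution (58 degrees of freedom, noncentrality d × √(30/2)) gives probabilities of 0.48 and 0.97 that the feature is declared different.

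Holding the SD at 1 is not consistent with the scenario. If a share p of a group has plasma and the matrices are 2 SD apart, the within-group variance is 1 + 4p(1 − p). The standardised difference is then d = 2(p₂ − p₁) / √(mean of the two variances):

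| Plasma share, group 1 vs group 2 | Variances | Mean variance | d | Probability |
|---|---|---|---|---|
| 0% vs 25% | 1.00, 1.75 | 1.375 | 0.43 | 0.37 |
| 25% vs 50% | 1.75, 2.00 | 1.875 | 0.37 | 0.29 |
| 37.5% vs 62.5% | 1.94, 1.94 | 1.94 | 0.36 | 0.28 |
| 0% vs 50% | 1.00, 2.00 | 1.50 | 0.82 | 0.87 |
| 25% vs 75% | 1.75, 1.75 | 1.75 | 0.76 | 0.82 |

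So 0.48 becomes about 0.28 to 0.37, and 0.97 becomes about 0.82 to 0.87. These are for a single feature at an unadjusted 0.05. A non-targeted screen would normally adjust for multiplicity, which would lower them.

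**The case the text supports.** If both matrices are drawn in everyone and analysed separately, the imbalance is zero. The spurious difference is then 2 × 0 = 0 SD.

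**The case for a change.** The best case for a change is that the choice of specimen belongs in the protocol. It cannot be deferred to a statistical analysis plan, because blood drawn into the wrong tube cannot be recovered. Correcting the text is nearly free before sampling: one word deleted, or one extra tube at the same draw. A non-targeted screen is also the setting in which an unrecognised matrix effect would be hardest to spot. Even the corrected probabilities of 0.28 to 0.87 are far above 0.05.

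Part of this stands. The lists do differ, no plasma collection is stated, and the collection list belongs in the protocol. What does not stand is the step from an incomplete list to a biased comparison, which needs partial collection, imbalance between groups and pooling of matrices. The document plans none of them. The further requests, to name a primary blood matrix and to forbid pooling, concern detail usually held in a statistical analysis plan or laboratory manual, and their absence from a short protocol is not an error. Analysing both matrices does increase the number of blood features tested, but that is a legitimate design choice.

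**Conclusion.** No change to the plan follows. The surviving point is a one-item inconsistency: plasma is on the analysis list and not on the collection list. It is best read as a clerical omission that the team would settle when preparing the blood draw, because samples cannot be ordered or processed without deciding which tubes to take. Following the methodology with all three specimens breaches nothing in the objectives and yields no wrong result. If plasma were not collected, the bone and serum comparisons, which are what Objective 1 asks for, would be unaffected.

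The effect on stated figures is nil, since the protocol gives none that depend on the specimen list. The 0.28 to 0.87 range describes a hypothetical in which every input is assumed, and should not be cited as a property of this study.

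The conclusion rests on two assumptions: that cases and controls have the same blood specimens taken, and that plasma and serum results are kept apart. The document does not say either outright, but its separate listing of the two matrices and its single collection instruction covering both groups point that way. Evidence that the groups were sampled in different matrices, or that the results were pooled, would reopen the question.
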